## RESEARCH PLAN

### A. Specific Aims

List the broad, long-term objectives and describe concisely and realistically what the specific research described in your proposal is intended to accomplish, and the hypothesis to be tested.

The long-term objectives of the study are to determine whether earlier administration of Belladonna and opium (B and O) suppositories ameliorates the discomfort associated with bladder spasms and reduces the need for oral narcotics and antimuscarinics in the post-operative setting.

Most patients who receive B and O suppositories in the post-operative period receive them in the PACU after expressing discomfort. The administration of B and O suppositories in these cases can often be hours from surgery end time.

The hypothesis to be tested is that giving patients B and O suppositories prior to surgery or post-operatively while still in the operating room will reduce the amount of pain medications that people will need post-operatively, reduce the amount of discomfort that patients experience from bladder spasms, and possibly reduce the length of hospital stay.

### B. Background and Significance

Briefly give the background to the present proposal, critically evaluate existing knowledge, and specifically identify the gaps which the project is intended to fill. Cite literature and include a list of references.

Bladder Spasms are a frequent cause of discomfort in the post-operative setting after lithotripsy, and while B and O suppositories are occasionally used post-operatively to relieve bladder spasms, there are no studies that show how effective they are. There are two studies that evaluated the use of B and O suppositories in a perioperative setting after robotic prostatectomies:

Lukasewycz S, Holman M, Kozlowski P, Porter CR, Odom E, Bernards C, Neil N, Corman JM. Does a perioperative belladonna and opium suppository improve postoperative pain following robotic assisted laparoscopic radical prostatectomy?

Results of a single institution randomized study. *Can J Urol.* 2010 Oct;17(5):5377-82. PubMed PMID: 20974030

These two studies show a possible benefit to perioperative belladonna and opium suppositories. However, these studies have never evaluated the use of the suppositories in lithotripsy procedures where the bladder is dilated and drained multiple times during a procedure. The constant distension leads to bladder spasms in the post-operative setting, which require narcotics and anti-muscarinics. There are also no studies to evaluate the effect of timing of administration of these suppositories in lithotripsy cases on postoperative pain, the use of narcotics in the post-operative period, and length of hospital stay.

#### C. Preliminary Studies

Provide an account of the PI/IS's preliminary studies pertinent to the protocol and/or any other information that will help to establish the experience and competence of the PI/IS to pursue the proposed project. The titles and complete references to appropriate publications and manuscripts submitted or accepted for publication may be listed.

There have not been any preliminary studies done by the PI on this subject. However [name] has several years experience dealing with lithotripsy patients in the post-operative setting. All attending physicians participating in this study have years of experience dealing with lithotripsy patients.

#### D. Research Design and Methods

Describe the research design and the procedures to be used to accomplish the specific aims of the project. Include the means by which the data will be collected, analyzed, and interpreted.

-1. Subjects will be identified as meeting inclusion criteria for this study during an office visit at the MFA urology clinic. Opportunity to participate in the study will be offered to the subject and informed consent obtained as appropriate. As noted above, patients will be informed of their right to not participate in the study. Ureteroscopy will still be offered to all patients who meet the appropriate indications, regardless of their participation in this study. Patients will be given a pre-operative survey to determine the severity of any bladder spasms they are

experiencing before surgery and to gauge their level of narcotic usage in the acute setting pre-operatively.

-2. The patients will be divided into three research arms. Patients will be randomly selected for one of the groups using a random number generator between 1 and 3. There will be a "Control Group" which will receive a rectal exam while still in the operating room in the lithotomy position after the procedure. There will be a "Postoperative OR" group which will receive a B and O suppository while still in the operating room in the lithotomy position after the procedure. Finally, there will be a "Preoperative OR" group which will receive a B and O suppository after the induction of anesthesia prior to beginning the urologic procedure in the lithotomy position. The "Control Group" will receive a rectal exam in the operating room after the procedure but before extubation to simulate the effects of suppository administration so that we know that any effects are due to the medication and not to the placement of the suppository itself. Those patients in the "control group" may receive a B and O suppository as part of standard procedure in the post-operative period if these individuals experience any bladder spasms and wish to have this as a treatment. This administration will be at the discretion of the operating surgeon as it is in standard cases. Patients may also receive Ditropan in the post-operative setting, which is part of the standard procedure for treating bladder spasms following urologic procedures. Patients in the postoperative and preoperative OR groups will be offered Ditropan for any bladder spasms in the post-operative setting to control symptoms, which is part of the normal standard of care for anyone who has already received a B and O suppository with inadequate control of symptoms. All patients will be treated with a normal post-operative pain regimen which may include narcotics. This will be at the discretion of the treating physician.

-3. In the post-operative setting, all subjects will be given a quick survey within 24 hours to assess their amount of discomfort related to bladder spasms/urinary discomfort. In addition, subjects medical charts will be reviewed to determine the amount of antimuscarinics that the patient received 24 hours post-operatively and the amount of narcotic and non-narcotic pain medication that subjects required. Patients not in the experimental arm will be given oral anti-muscarinics to treat any bladder spasms that they may have, but will not be given suppositories.

-4. Data will be entered into the database following the procedure as available.

-5. Subjects will have clinically appropriate follow-up per the attending urologist. If, as part of that follow-up, clinically relevant events occur, the corresponding data will be recorded in the database.

Note that, with the exception of which particular study arm the subjects are enrolled into and the recording of data as detailed above and below, there will be absolutely

no difference in the care received by patients choosing to participate in this study and those who elect not to participate.

Data will be analyzed using commercially available statistical software. T-tests will be performed for continuous variables and Pearson's Chi-squared tests for categorical variables. Analysis will be tailored to compare B and O Supprenettes Suppositories and placebo/no suppository in order to best answer the research question.

1. Describe any new methodology and its advantage over existing methodologies.

There are no methodologies in this protocol which are new.

2. Discuss potential difficulties and limitations of the proposed procedures and alternative approaches to achieve the aims.

The procedure is designed so that patients receive a B and O suppository as they would as part of standard protocol in the post-operative period if bladder spasms were experienced. The only difference is regarding timing of administration. Therefore, there are no potential difficulties or limitations of the proposed procedure since B and O administration is already a well-accepted treatment for bladder spasms following urologic procedures.

3. Provide a tentative sequence or time table for the study.

November 2015 - IRB approval and begin recruiting patients for study

December 2015 - June 2016 Conducting study according to aforementioned protocol

July 2016 - Begin data analysis and manuscript preparation

4. Specify procedures, situations, or materials that may be hazardous to personnel and the precautions to be taken to ensure safety.

None

5. Provide justification of the sampling procedure and sample size. Gender and Minority Inclusion, it is required that all research involving human subjects and human materials include minorities and women, as well as males and females of all ages. If one gender and/or minorities are excluded or are inadequately represented in a protocol, particularly in proposed population-based studies, a clear compelling rationale for exclusion or inadequate representation should be provided. The composition of the study population must be described in terms of gender and

racial/ethnic group, together with a rationale for its choice (by age distribution, risk factors, incidence/prevalence, etc.)

All participants undergoing lithotripsy procedures at GW hospital with the included physicians will be asked to participate in the study.

We determined the expected effect sizes based on previous studies of this same treatment in patients who received robot-assisted laparoscopic surgery for prostate CA.

Based on morphine equivalent dose in both Scavonetto, Lamborn, McCaffrey et al. (Can J. Urol 2013) and Lukaswycz, Holman, Kozlowski et al. (Can J Urol 2010), we would like to detect a 4 mg eq. difference between groups, with an expected standard deviation (sd) of 5, i.e., an effect size (d) of 0.8. For post-op pain rated on a 10-point scale both of the previous studies found sd ~2.0. We would like to detect a 1-point difference, so will power for an effect size of 0.5. Scavonetto et al. found approximately 20% of patients required use of rescue B&O suppositories and 60% requiring Oxybutynin for post-op bladder spasm. Thus, for this outcome we will try to detect a difference in percent positive of 20%. For all comparisons, we will use 2-tailed tests with alpha=.05.

Immediate post-op morphine equivalent dose.

In order to have power >.80 to detect an effect size of 0.8 in morphine eq. dose, we would need n=26 per group, or total N=51. For power >.90, we would need 34 per group or total N=68.

Post-op pain.

For an effect size of 0.5, in order to have power >.80, we would need 64 per group, or total N=128. For power >.90, we would need 86 per group, or total N=172.

Use of medication for bladder spasms.

Here, we will want to detect a 20% difference between groups. Assuming that in the treatment group, 20% of patients need rescue medication for bladder spasm, while 40% need such meds in the control group, we would need n=82 per group (total N=164) in order to detect a difference this large with power >.80.

Therefore, in order to have adequate power across all 3 outcome measures, we plan to enroll a total of 180 subjects, randomized equally across treatment and control groups.

6. Identify all drugs and devices to be used, if applicable,. If the drug or device is investigational under FDA policy, list the actual IND/IDE number and respective source, supplier, and/or sponsor. If an IND/IDE has been assigned provide the FDA

stage status. Note the proposed dosage related information including instructions for administering, adverse effects, compatibility in infusions, and stability.

Please see package inserts for B and O suprette suppositories attached to this submission. We are also including Ditropan, which is the oral anti-muscarinic to be included in this study. The dosage of B&O will be 16.2mg/30mg which is in the formulary at GW. Ditropan will be given in the normal 5 mg dosage.

7. Identify all procedures that will be used for the purpose of this research. If blood is to be drawn, indicate amount to be withdrawn per single withdrawal, and the total amount of blood to be drawn. If transfusions are anticipated, include assurance that the volume of blood removed for research purposes will not necessitate a transfusion. [Refer to Section 1.5.5]

E. Study Population –(Gender and Minority Inclusions):

1. Describe the characteristics of the subject population, include the anticipated number of normal volunteers, age ranges, sex, ethnic background, and health status.

Identify the criteria for inclusion or exclusion (especially women and/or minorities).

Explain the rationale for the use of special classes of subjects, such as fetuses, pregnant women, or others who are likely to be vulnerable, especially those whose ability to give voluntary informed consent may be questionable.

The subject population will be patients seen at GW for lithotripsy procedures. This will include men and women ages 18-89. It will include all ethnic backgrounds, and anyone who has been cleared for surgery.

The criteria for exclusion for those patients who agree to participate in the study will be patients with glaucoma, severe hepatic or renal disease, bronchial asthma, respiratory depression at the time of administration, convulsive disorders, allergy to anti-muscarinics or opiates, history of anorectal surgery, pre-operative use of antimuscarinics, chronic pain, chronic use of analgesics, or a history of alcohol or opioid dependency, pregnant women and nursing mothers.

F. Human Subjects (Risks & Benefits)

1. Identify sources of research material obtained from individually identifiable living human subjects in the form of specimens, records or data. Indicate whether the material or data will be obtained specifically for research purposes or whether use will be made of existing specimens, records or data. Subjects with specific diseases or conditions are often identified as potential subjects through some type of record

(e.g., medical records, patient charts, registries for cancer cases, surgical or X-ray log books, school records). Controls may come from the same population as the subjects (which is always the case in a randomized clinical trial), be persons with unrelated conditions or be volunteers from the general population.

No material from individual human subjects will be used. All information obtained will be through patient surveys and the patient's medical records.

2. Describe plans for recruitment of subjects and the consent procedures to be followed; including the circumstances under which consent will be sought and obtained, who will seek it, who will give consent, the age range of the individual who will give consent, the nature of the information to be provided to prospective subjects, payment for participation (if applicable), the prospective subjects, and the method of documenting consent. (State if you are requesting a 'waiver of consent' from the IRB and why.) [Refer to Section 3.0]

Subjects will be recruited from patients who are determined to need a lithotripsy procedure with the above attending Urologists. They will be asked to consent to participate in the study at some time before their procedure. This could be in the clinic weeks beforehand, this could be in the ER when the patient presents with a stone, and it could be pre-operatively while the patient is being consented for the procedure. The consent will be done in a quiet area one on one with the patient and the patient will be given time to ask questions. The consent form, which is attached, will be given to the patient.

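### Section D gives two incompatible rules for post-operative B and O suppositories in the control group; secondarily, it does not say how B and O doses count in the medication outcomes

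*Combined protocol and SAP*

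**What the plan says.** **Control-arm rule.** Section D, item 2, sets up three arms. Controls have a rectal exam in the operating room. Afterwards, control patients who have spasms and want the treatment "may receive a B and O suppository as part of standard procedure in the post-operative period", at the operating surgeon's discretion. Item 3 says of everyone outside the experimental arm that they "will be given oral anti-muscarinics to treat any bladder spasms that they may have, but will not be given suppositories".

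**Randomised doses.** The Postoperative OR group "will receive a B and O suppository while still in the operating room in the lithotomy position after the procedure". The Preoperative OR group "will receive a B and O suppository after the induction of anesthesia prior to beginning the urologic procedure". Section D.6 gives the strength: "The dosage of B&O will be 16.2mg/30mg which is in the formulary at GW".

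**Medication outcomes.** Item 3 has charts reviewed for "the amount of antimuscarinics that the patient received 24 hours post-operatively and the amount of narcotic and non-narcotic pain medication" that subjects required. Section D.5 powers an immediate post-operative morphine-equivalent dose: "we would like to detect a 4 mg eq. difference between groups, with an expected standard deviation (sd) of 5". It also powers the proportion of patients who use medication for bladder spasms.

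**Comparison.** Section A asks about earlier administration, against a usual practice in which the suppository is given in the PACU after the patient reports discomfort. Section B names as unstudied the "effect of timing of administration of these suppositories in lithotripsy cases on postoperative pain, the use of narcotics in the post-operative period". The data-analysis paragraph in section D describes the comparison as B and O against placebo or no suppository. The limitations paragraph that follows says that only the timing of the suppository differs from standard care.

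**The concern.** Items 2 and 3 describe the same patients, the same period and the same drug, and they give opposite instructions. Under item 2 the trial compares early with on-demand B and O. Under item 3 it compares B and O with oral treatment only. These are different questions, and the answer to one need not carry over to the other. If surgeons differ in which sentence they follow, the control arm becomes an unplanned mixture.

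The second issue is measurement. The study drug belongs to both drug classes that the trial counts as outcomes, and every active-arm patient receives one dose by design. If that dose is counted, part of the hoped-for reduction is offset by the treatment itself. If it is counted in one active arm and not the other, a difference between the timing arms appears that no treatment effect caused.

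**Working it through.** **1. Can items 2 and 3 both be true?**
- Item 3 is about treating spasms after surgery, so it cannot be limited to the dose given in the operating room.
- The experimental arm is singular and undefined in a three-arm design, but every reading leaves the control group outside it.
- Item 3 cannot mean non-participants. It follows a description of what all subjects undergo, and section D elsewhere says that non-participants' care differs only in arm assignment and data recording.

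The two rules therefore conflict.

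**2. Does another section settle it?**

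| Text | Fits item 2 | Fits item 3 |
|---|---|---|
| Section A: earlier administration against the usual PACU dose | yes | no |
| Section D, limitations: timing is the only difference | yes | no |
| Section D, analysis: placebo or no suppository | no | yes |

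More of the text fits item 2, but item 3 is explicit and the analysis wording agrees with it.

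**3. Counting rule.**
- *Opioids.* Section A speaks of the need for oral narcotics, and item 3 of pain medication required. A rectal dose assigned by randomisation is neither, so the wording leans towards excluding it. It does not say so, and it does not cover a later B and O dose.
- *Antimuscarinics.* Item 3 speaks of the amount received in the 24 hours after surgery, with no stated start. Counting from the end of the procedure would catch the Postoperative OR dose but not the Preoperative OR dose. Counting from PACU arrival would catch neither.

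**4. What counting the opioid is worth (illustration).**

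Inputs from section D.5: difference 4 mg, SD 5, two-sided alpha 0.05, and 180 patients allocated equally. With three arms this is 180/3 = 60 per arm.

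The plan's own figure: d = 4/5 = 0.8, and the exact two-sample t-test needs 25.5 per group for power 0.80. This reproduces the stated 26 per group (total 51).

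Assumptions: the opium in one suppository is worth c mg morphine equivalents (no conversion is given in the documents), the planned 4 mg excludes it, and controls receive no B and O. If the randomised dose is counted, the contrast is 4 − c and d = (4 − c)/5. Power is from the noncentral t distribution:

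| c (assumed) | d | Power, 60 v 60 | Power, active arms pooled, 120 v 60 |
|---|---|---|---|
| not counted | 0.8 | 0.99 | >0.99 |
| 1 mg | 0.6 | 0.90 | 0.97 |
| 2 mg | 0.4 | 0.58 | 0.71 |
| 3 mg | 0.2 | 0.19 | 0.24 |

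**The case against.** The strongest reply is that the plan's intent can be recovered. Sections A and D mostly describe early against on-demand B and O, and the opioid wording points away from counting the randomised dose. Section O has the study suppository entered as a research drug, scan-coded and logged, so those doses can be separated at analysis. The value of c is an assumption, and nothing in the plan says that the dose will be counted.

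Much of this stands. It makes the counting gap secondary and confines the power figures to illustration. It does not remove the contradiction, because a surgeon who reads item 3 is told not to give what item 2 allows. Logging shows which doses were given, not which ones count.

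Two stronger readings are tempting, and the documents do not support them:
- *That the result could not be attributed to any comparison.* The randomised contrast remains early B and O against whatever controls received. What is lost is a fixed description of the control condition.
- *That the 24-hour window would create a false difference in morphine equivalents between the two active arms.* The window is attached directly only to antimuscarinics, the powered opioid outcome is described as immediate, and no test of pre-operative against post-operative dosing is written.

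**Conclusion.** The contradiction between items 2 and 3 is clear on the face of the text, and the protocol cannot be followed consistently as written. It must be resolved. This conclusion needs no numerical assumption.

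The counting gap is real but smaller. It is open for antimuscarinics, where the window could treat the two active arms differently. For opioids the wording leans towards exclusion without stating it. The power losses in the table apply only if the randomised dose is counted, c lies in the assumed range, and the planned 4 mg excludes the suppository. They show what the choice is worth and do not predict a result.

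The stated sample sizes are not called into question here. The appendix and consent form were not available. They might contain a counting rule, but they would not remove the conflict within section D.

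**What to change.** 1. Reconcile items 2 and 3 of section D so that one control-arm rule for post-operative B and O holds throughout. Which rule is the sponsor's clinical decision.
2. Reword the comparison in the data-analysis paragraph to name the randomised arms, consistently with that rule.
3. Before analysis, write one counting rule, identical in all arms, that says whether the randomised dose and any later B and O dose enter each medication outcome. List randomised B and O doses separately from later medication.
4. State when the 24-hour window starts and which outcomes it covers, so that both active arms are treated alike. If any opium is counted, state the conversion.

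The cost is protocol wording and one chart-abstraction rule, with no additional patients or data.

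### Two powered outcomes depend partly on discretionary prescribing by several attendings, but the planned tests leave surgeon out: a modest loss of precision, not bias

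*Combined protocol and SAP*

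**What the plan says.** Section D (Research Design and Methods), item 2, says of the postoperative pain regimen, narcotics included: "This will be at the discretion of the treating physician". The same item leaves a rescue suppository in the control arm to the operating surgeon's judgement. Drug use over the first 24 hours is then taken from the chart (item 3).

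More than one attending is involved. Sections C and F.2 refer to them in the plural, and the sample-size section (D.5) says that lithotripsy patients "with the included physicians will be asked to participate in the study". Their number and caseloads are not given.

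Allocation is made "using a random number generator between 1 and 3", with no strata or blocks mentioned. The analysis paragraph of section D says "T-tests will be performed for continuous variables" and names Pearson's chi-squared for categorical variables. It adds that the analysis will be tailored to suppository versus no suppository, but names no covariate. No common analgesic protocol or order set is described.

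**The concern.** Morphine-equivalent dose and use of spasm medication record what was ordered and given. If one attending's patients routinely receive more narcotic or antimuscarinic than another's, that spread enters the outcome whatever the arm. An unadjusted test treats it as unexplained noise, and under simple randomisation the surgeon mix can differ somewhat between arms by chance.

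What is at stake is interval width and power. That matters most for spasm medication. If the planned 180 are split equally over three arms, a comparison of one active arm with control has 67% power for that outcome, below the plan's own target of more than 80%. A baseline factor that costs nothing to record is then worth considering.

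**Working it through.** **Inputs from the plan (section D.5).**
- Test level: "For all comparisons, we will use 2-tailed tests with alpha=.05".
- Morphine equivalents: "we would like to detect a 4 mg eq. difference between groups, with an expected standard deviation (sd) of 5", so d = 4/5 = 0.8.
- Pain: "We would like to detect a 1-point difference, so will power for an effect size of 0.5".
- Spasm medication: 20% on treatment against 40% on control.
- Total 180. Three equal arms give 180/3 = 60 per arm.

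**Step 1. Reproduce the plan's own figures.**
- Morphine: the normal approximation is 2(1.960 + 0.842)²/0.8² = 24.5. The exact noncentral-t solution is 25.5 per group, 51.05 in total. The plan says "we would need n=26 per group, or total N=51". It agrees.
- Pain, d = 0.5: noncentral t gives 63.8, so 64 per group. It agrees.
- Spasm medication: [1.960√(2·0.3·0.7) + 0.842√(0.4·0.6 + 0.2·0.8)]²/0.2² = 81.2, so 82 per group. It agrees.

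**Step 2. Power at 60 v 60, unadjusted.**
- Morphine 99.1% and pain 77.5% (noncentral t).
- Spasm medication: z = (0.2√60 − 1.960·0.648)/0.632 = 0.44, so power is 67.0%.

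**Step 3. What a surgeon term does for morphine dose.** Let ρ be the share of outcome variance explained by surgeon. The documents do not give it; 0.05, 0.10 and 0.20 are assumed, with the stated SD of 5 taken to include it. Adjustment multiplies the SD by √(1−ρ).

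| ρ | √(1−ρ) | n per group for 80% power | power at 60 v 60 |
|---|---|---|---|
| 0 | 1 | 26 | 99.1% |
| 0.05 | 0.975 | 25 | 99.4% |
| 0.10 | 0.949 | 24 | 99.6% |
| 0.20 | 0.894 | 21 | 99.8% |

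Intervals narrow by 2.5%, 5% and 11%; power rises by less than 1 point. If the SD of 5 does not include the spread between physicians, the SD becomes 5/√(1−ρ) = 5.13 to 5.59 and the requirement rises from 26 to between 27 and 32 per group. That is still well under 60.

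**Step 4. Chance imbalance.** The shift in the morphine difference caused by uneven surgeon mix has SD of about 5√ρ·√(2/60) = 0.20, 0.29 and 0.41 mg for the three values of ρ, against a 4 mg target. In simulated trials with 3, 4 or 6 equal-volume surgeons, the unadjusted t-test kept a type I error of 0.047 to 0.053.

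**Step 5. Spasm medication, by simulation.** The settings are 180 patients, simple three-way allocation, four equal-volume surgeons, and treatment halving each surgeon's control rate (the plan's 40% to 20% on average). The surgeon-specific rates are assumed. The comparison is one active arm against control.

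| Control rates by surgeon | Chi-squared | CMH, no correction | CMH, with correction |
|---|---|---|---|
| 20, 30, 50, 60% | 0.67 | 0.69 | 0.61 |
| 10, 20, 60, 70% | 0.66 | 0.74 | 0.66 |
| all 40% | 0.67 | 0.66 | 0.58 |

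Repeat simulations agree to within about 0.01. The uncorrected Cochran-Mantel-Haenszel (CMH) test changes power by about +2, +8 and −1 points. With the continuity correction the adjusted test is never better than the planned one, and is usually worse.

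**The case against.** The strongest reply is that nothing here is an error. Patients are randomised individually, so the planned tests are valid and chance differences in surgeon mix are already allowed for in the p-value. That stands.

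A reader might infer that surgeon mix biases the comparison, or that it is a leading rival explanation for any arm difference. The documents do not support either. Allocation does not depend on surgeon, and the shifts in Step 4 are small beside the 4 mg target. Nor can the gain be stated as a firm number of patients saved, because the surgeon effect appears nowhere in the documents.

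It is also fair that the benefit is small where the argument applies most directly. Morphine-dose power has almost no room to rise, and the 8-point gain for spasm medication needs surgeon rates ranging from 10% to 70%. Pain is patient-reported and depends on prescribing only indirectly, so it is not counted here.

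Two further points stand. The plan names the treating physician for narcotics and the operating surgeon for control-arm rescue, and never says they are the same person, so a surgeon term may miss part of the variation. And separate blocked lists per surgeon would make the next assignment easier to guess, since whoever performs the rectal step knows the arm and no concealment procedure is described.

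Finally, a surgeon term would not address rescue arrangements that differ by arm. Item 2 of section D allows control patients a suppository, while item 3 says patients outside the experimental arm will not be given one. Those passages must be reconciled separately.

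**Conclusion.** The concern holds as a matter of efficiency. Two powered outcomes depend partly on discretionary prescribing by several attendings, and the planned analysis does not use surgeon. The consequence is a loss of precision whose size the documents do not fix.

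On the assumptions above (60 per arm, four equal-volume surgeons, the listed rates), adjustment is worth about −1 to +8 points of power for spasm medication. For ρ of 0.05 to 0.20, it is worth under 1 point of power and intervals 2.5% to 11% narrower for morphine dose. The 60 per arm is itself a reading of the plan. If both active arms were pooled (120 v 60), unadjusted power for spasm medication would be about 81% and the need less pressing. This is a cheap improvement worth making, and the planned tests remain valid without it.

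**What to change.** Record the attending surgeon scheduled for each patient, pool low-volume surgeons into one category, and state before the data are examined that surgeon is a factor in the analysis:
- Continuous outcomes: a linear model with arm and surgeon in place of the t-test.
- Spasm medication: a Cochran-Mantel-Haenszel test stratified by surgeon, explicitly without continuity correction, reported with a surgeon-stratified risk difference.

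The cost is one recorded field and two or three sentences of analysis text. The statistical downside is about 1 to 2 points of power for spasm medication if surgeons do not differ. The adjustment will remove only part of the prescribing variation if narcotics are ordered by someone other than the surgeon.

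Stratifying the allocation list by surgeon is optional. It is worthwhile only if allocation is concealed, because blocked lists per surgeon are otherwise easier to predict than the planned independent draw. The analysis change does not depend on it and can be adopted even if allocation has begun.
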